9.3. Analysis Population

The following analysis populations are planned:

- Safety population: All randomized subjects
- Full Analysis (FA) population: All randomized subjects
- Per-protocol (PP) population: Subset of the Full Analysis Set and excludes subjects with major protocol violations, entry criteria violations or missing visits. The results of the Full Analysis Set will be considered primary.

9.4. Data Analysis

9.4.1. Subject Disposition

The number and percentage of subjects included in each population, who completed the study, who discontinued study and reason for discontinuation will be presented for each cohort and treatment.

9.4.2. Demographics and Baseline Characteristics

Demographic and baseline characteristics will be presented for each population by Treatment arm.

9.4.3. Primary Endpoints

For the primary endpoint, the proportion of subjects alive and free of respiratory failure at Day 28, the number and percentage of subjects will be presented by group. Possible differences between groups will be assessed using a generalized linear mixed model, assuming a binomial distribution and a logit link. The model will include group as a fixed effect. Subjects who discontinue the study prior to Day 28 will be considered treatment failures.

9.4.4. Secondary Endpoints (Safety)

AEs will be coded using the Medical Dictionary for Regulatory Activities (MedDRA) and will be summarized by System Organ Class (SOC) and Preferred Term for each group. The first occurrence will be tabulated for an event that occurred more than once for a subject.

Additionally, AEs will be tabulated by maximum severity and nearest relationship to IP. SAEs will be summarized similarly to AEs.

For continuous safety endpoints, descriptive statistics (number of subjects, mean, standard deviation, minimum, median and maximum values) will be presented by group and study day. The changes from Day 1 to each subsequent day will be calculated for each subject and descriptive statistics will be presented. Possible differences between groups will be assessed using a mixed effect model repeat measurement (MMRM) analysis of covariance. The model will include the Day 1 value as a covariate, fixed effects of group, study day and group-by-study day interaction with subject as a random effect.

Categorical safety endpoints will be summarized as the number and percentage of subjects per category for each group.

Treatment-emergent adverse events (TEAE) will be defined as any AE occurring post first administration. Adverse events will be presented for each cohort and treatment by System Organ Class (SOC) and Preferred Term (PT):

- Treatment-emergent adverse events (TEAE): defined as any AE occurring postdose administration through 28 days following IP administration.
- IP related TEAEs
- SAEs
- IP related SAEs
- TEAEs (by grade and relationship to IP)
- Laboratory abnormalities by toxicity grade

9.4.5. Secondary Endpoints (Efficacy)

The proportion of subjects alive and discharged from the ICU at Day 14 and Day 28 and the proportion alive and free of respiratory failure at Day 60 and will be presented and analyzed as described for the primary efficacy endpoint. Subjects who discontinue from the study prior to each study day will be considered treatment failures.

Clinical Status will be assessed using a generalized linear mixed model, assuming a multinomial distribution. The model will include the Day 1 value as a covariate with fixed effects of group,

study day and group-by-study day interaction and subject as a random effect. If the group-by-study day interaction is found to be statistically significant then comparisons between groups at Day 7, Day 14 and Day 28 will be obtained from this model. Additionally, stacked bar charts will be presented for the proportion of subjects in each category by group and study day.

For the time from randomization to first occurrence of respiratory failure or death on study due to any cause, the Kaplan-Meier method will be applied. Subjects will be censored at the time of last follow-up. For each group, the 25th percentile, median and 75th percentile will be presented, if possible. Possible differences between groups will be assessed by the log-rank test.

The total number of deaths per group will be presented for All-cause mortality at Day 90.

9.4.6. Exploratory Endpoints

For all other efficacy endpoints, descriptive statistics (number of subjects, mean, standard deviation, minimum, median and maximum values) will be presented by group and study day. The changes or percent changes from Day 1 to each subsequent day will be calculated for each subject and descriptive statistics will be presented. Possible differences between groups will be assessed using a MMRM analysis of variance\covariance. The model will include fixed effects of group, study day and group-by-study day interaction with subject as a random effect. The Day 1 value will be included when appropriate.

9.4.7. Interim Analysis

An interim futility analysis will be performed after 40 subjects have been enrolled. The analysis will be performed by an independent biostatistician who will have no contact with the study team.

10. ADVERSE EVENT DEFINITIONS AND PROCEDURE FOR RECORDING, EVALUATING, FOLLOW-UP AND REPORTING

10.1. Monitoring, Recording and Reporting of Adverse Events

An adverse event (AE) is any noxious, unintended, or untoward medical occurrence that may appear or worsen in a subject during the course of a study. It may be a new intercurrent illness, a worsening concomitant illness, an injury, or any concomitant impairment of the subject's health, including laboratory test values (as specified by the criteria below), regardless of etiology. Any worsening (i.e., any clinically significant adverse change in the frequency or intensity of a pre-existing condition) should be considered an AE. A diagnosis or syndrome should be recorded on the AE page of the CRF rather than the individual signs or symptoms of the diagnosis or syndrome.

An overdose, accidental or intentional, whether or not it is associated with an AE, or abuse, withdrawal, sensitivity or toxicity to an investigational product should be reported as an AE. If an overdose is associated with an AE, the overdose and AE should be reported as separate terms. All subjects will be monitored for AEs during the study. Assessments may include monitoring of any or all of the following parameters: the subject's clinical symptoms, laboratory, pathological, radiological or surgical findings, physical examination findings, or findings from other tests and/or procedures.

All AEs will be recorded by the Investigator from the time the subject signs informed consent until 28 days after hospital discharge. AEs that lead to study discontinuation should be followed until resolution or stabilization.

Serious Adverse Events (SAEs), regardless of relationship to investigational product, that occur from the time the subject signs informed consent until the last study visit and those made known to the Investigator at any time thereafter must be reported to Drug Safety within 24 hours of the Investigator's knowledge of the event.

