Subjects who discontinue at any time after randomization will not be replaced. There is no treatment crossover in this study.

Once subjects provide informed consent, they will have screening assessments performed (up to a 7-day screening window). Study Day 1 is the day of randomization. Subjects randomized should receive their first dose of STI-5656 or placebo on the day they are randomized (Day 1).

Subjects will be assessed daily while hospitalized. Subjects in both arms are assessed for adverse events and toxicities and all adverse events should be reported regardless of treatment arm assignment or causality.

PK samples will be collected from the first 20 subjects enrolled in this trial. For sampling time points please refer to the schedule of assessments.

Subjects will have an outpatient visit on Day 28 (for various study procedures) and a telephonic contact on Day 60 to collect any additional AEs and follow-up for unresolved AEs to resolution or to establishment of a new baseline.

SOC treatments will be collected in the electronic case report form (e-CRF) until hospital discharge. Continued outpatient treatment (concomitant medications) will be collected until Day 28. Any investigational medication received will be collected until Day 90.

Note: Investigational medicines other than STI-5656 are prohibited up to Day 28 or hospital discharge.

Discharged subjects will be contacted at Day 60 and Day 90 to collect survival, any experimental treatments and additional hospitalization information since the study hospital discharge.

[figure not shown]
Subjects should be encouraged to remain in the study even if Study Drug is discontinued (for any reason).

Statistical Design

An evaluable sample size of 40 subjects per group (treatment arm) will provide 80% power ($\alpha=0.05$, 2-sided) to detect a difference between groups in the number of subjects alive and free of respiratory failure at Day 28. This assumes that 95.7% of subjects who received STI-5656 plus SOC (group 1) and 70% of subjects who received only SOC (group 2) will be alive and free of respiratory failure at Day 28. This represents a treatment effect difference of approximately 26%.

All tests of significance will be assessed at alpha level=0.05, 2-sided.

Figure 1: Study Design

Schedule of Assessments (SOA)

See [Table 1](#) for SOA

Data Monitoring Committee

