2. SCHEDULE OF ASSESSMENTS (SOA)

Table 1: Schedule of Assessments

Assessments	Screening (Day -4 to -1)	Day 1 (Dose 1) ¹	Daily until hospital discharge	Hospital discharge or Early Term ²	Outpatient visit: Day 28	Telephone Follow-up at Day 60 and 90
Informed Consent	X					
Assess eligibility	X	X				
Demographics ³	X					
RT-PCR assay for SARS-CoV-2 ⁴	X					
Medical history (including COVID-19 history)	X					
Concomitant medications	X	X	X	X	X	
Physical exam, including weight; height ⁵	X			X	X	
Vital signs ⁶	X	X	X	X	X	
12-lead ECG (performed locally) ⁷	X	X				
Pregnancy test for FCBP only ⁸	X	X		X	X	
Urinalysis ⁹	X	X	X		X	
Blood for hematology, coagulation and chemistry ¹⁰	X	X	X	X	X	
Blood for CRP, serum ferritin, VEGF-A and cytokines ¹¹	X	X	X	X	X	
Day 3, 5, 7, 10, 14 and 28 only						
Respiratory Status ¹²	X	X	X	X		
Adverse Events ¹³	X	X	X	X	X	
Assess clinical status ¹⁴	X	X	X	X		
IRT entry (at screening, randomization, then early termination or study completion	X	X		X		X
Study Drug administration (QD p.o.)		X	X ¹⁵			

Assessments	Screening (Day -4 to -1)	Day 1 (Dose 1) ¹	Daily until hospital discharge	Hospital discharge or Early Term ²	Outpatient visit: Day 28	Telephone Follow-up at Day 60 and 90
Sampling for pharmacokinetics ¹⁶	X ¹⁶	X ¹⁶	X ¹⁶			
Survival and additional experimental meds/ hospitalization/ICU status					X	X

Abbreviations: AEs: adverse events; ALC: Absolute lymphocyte count; ALT: alanine aminotransferase; AST: aspartate aminotransferase; CRP: C-reactive protein; BUN: blood urea nitrogen; CMP: complete metabolic panel; COVID-19: Coronavirus Disease 2019; D: day; ECG: electrocardiogram; ECMO: extracorporeal membrane oxygenation; ET: Early Termination; F: Fahrenheit; FCBP: female of childbearing potential; FiO₂: Fraction of inspired oxygen; IRT: Interactive Response Technology; IL: Interleukin; IFN γ : interferon gamma; QD: once daily; PaO₂: partial pressure of oxygen in arterial blood; p.o.: by mouth; RBC: red blood cells; rbc/hpf: red blood cells per high power field; RRT: rapid response team; RT- PCR: Reverse transcription polymerase chain reaction; TNF α : tumor necrosis factor alpha; WBC: white blood cells

¹ All assessments on Day 1 are to be performed prior to first dose of STI-5656. Day 1 laboratory results do not need to be available prior to randomization (and first dose of STI-5656 if assigned to that arm) if lab results are available from the previous 24 hours

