4. INVESTIGATIONAL PLAN

4.1. Overall Study Design

This is a Phase 2, randomized, double-blind, placebo-controlled, 2-arm multicenter study to assess the safety and efficacy of oral STI-5656 (or placebo) in the setting of current SOC in subjects with RT-PCR confirmed SARS-CoV-2 infection and COVID-19 pneumonia (documented radiographically) requiring hospitalization. Subjects must have oxygen saturation levels <94% on room air or subject requires supplemental oxygen.

Eighty (80) subjects meeting eligibility criteria will be randomized at a 1:1 ratio to one of two treatment arms in addition to SOC treatments:

- Arm 1: STI-5656
- Arm 2: Placebo

The STI-5656 dose is 100 mg p.o. QD administered up to 14 days or until hospital discharge if sooner.

SOC treatments will be collected in the electronic case report form (e-CRF).

Subjects who discontinue at any time after randomization will not be replaced. There is no treatment crossover in this study.

Once subjects provide informed consent, they will have screening assessments performed (up to 4-day screening window). Study Day 1 is the day of randomization. Randomized Subjects should receive their first dose of Study Drug on Day 1.

Subjects will be assessed daily while hospitalized. Subjects in both arms are assessed for adverse events (AEs) and toxicities and all AEs should be reported regardless of treatment arm assignment or causality. Subjects will be contacted on Day 28 to collect any additional AEs and follow-up for unresolved AEs,

SOC treatments will be collected in the electronic case report form (e-CRF) until hospital discharge. Continued outpatient treatment (concomitant medications) will be collected until Day 28. Any investigational medication received will be collected until Day 90. Note: Investigational medicines other than STI-5656 are prohibited up to Day 28 or hospital discharge.

Discharged subjects will be contacted at Day 60 and 90 to ensure survival and collect any experimental treatments and additional hospitalization information since the study hospital discharge. Subjects on Treatment Arm 1 (STI-5656) should be encouraged to remain in the study even if Study Drug is discontinued (for any reason).

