8.1.11. Adverse Events

Adverse events will be collected from the time of signing the ICF through Day 60.

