8.2.4. Hospital Discharge or Early Termination from Study

- Physical Exam
- Vital Signs
- Clinical laboratory tests per [Section 8.1.7](#)
- Respiratory Status
- Collect adverse events
- Collect con meds
- Clinical status using 8-category ordinal scale of patient health status
- If early termination, register in IRT

8.2.5. Outpatient Follow-up Day 28

- Collect AEs, and update status on previously unresolved AE status
- Clinical laboratory tests per [Section 8.1.7](#)
- Collect survival, experimental medications since hospital discharge, any new hospitalizations/ ICU stays

8.2.6. Telephone Follow-up Day 60

- Update status on previously unresolved AEs
- Collect survival, experimental medications since hospital discharge, any new hospitalizations/ ICU stays

8.2.7. Telephone Follow-up Day 90

- Update status on previously unresolved AEs
- Collect survival, experimental medications since hospital discharge, any new hospitalizations/ ICU stays

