### **10.0 SAFETY EVALUATION**

#### **10.1 Adverse Events**

Treatment-emergent adverse events (TEAE) will be defined as any AE occurring post first administration of study drug. AEs will be coded using the MedDRA dictionary.

A summary of TEAEs will be presented as the number and percentage of subjects with at least one of the following:

- Any AE
- Any TEAE
- TEAE by Severity
- TEAE by Causality
- TEAEs leading to study discontinuation

- TEAEs leading to death (with outcome of Fatal)
- SAEs
- SAEs by Causality

AEs and TEAEs will be summarized by SOC and preferred term by treatment group. For subjects with the same SOC and preferred term occurring more than once, the first occurrence will be tabulated. AEs and TEAEs will also be presented for each preferred term by maximum severity, by nearest relationship to study drug, and for serious AEs.

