Chemistry: performed locally. 14-analyte complete metabolic panel (CMP): Albumin, alkaline phosphatase (ALP), alanine aminotransferase (ALT), aspartate aminotransferase (AST), bicarbonate, total bilirubin (TBIL), blood urea nitrogen (BUN), calcium, chloride, creatinine, glucose, potassium, sodium, total protein, D-dimer, fibrinogen.

 Cytokines include TNF $\alpha$ , IFN $\gamma$ , IL-6, IL-1 $\beta$ , IL-7, IL-8, IL-10, IL-12, IL-17, IL-18, IP 10, VEGF-A

 Record FiO2 (and PaO2) at the time of arterial blood gas sampling. If PaO2 is not available, use SpO2. Other respiratory status data to collect includes oxygen supplementation status: mechanical ventilation, face mask, nasal cannula or room air. Radiographic findings will also be collected.

 AEs will be collected from the time of informed consent to Day 60. Any ongoing AEs at Day 28 will be followed until resolution or stabilization.

 An 8-category ordinal scale of patient health status ranges: 0=no clinical or virological evidence of infection; 1=no limitation of activities; 2=limitation of activities; 3=hospitalized, no oxygen therapy; 4=oxygen by mask or nasal prongs; 5=non-invasive ventilation or high-flow oxygen; 6=intubation and mechanical ventilation; 7=ventilation + additional organ support – pressors, rapid response team (RRT), extracorporeal membrane oxygenation (ECMO); 8=death. See Section 18.2 for form.

 STI-5656 or placebo administration up to Day 14 or hospital discharge, whichever is sooner for subjects in Treatment Arm 1. Study drug capsules should be taken orally with 200-250 mL of water following at least 2 hours of fasting.

 Samples will be collected from the first 20 subjects enrolled. Sampling timepoints are as follows: Day 1 (predose) and at 0.5, 1, 2, 4, 8, 12, postdose on dosing days 1 and 8.

CONFIDENTIAL

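### The protocol gives two end points for AE collection (28 days after discharge, and Day 60) and contradicts itself on the Day 60 call; if 10.1 is followed, the non-serious AE window varies with length of stay

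*Protocol*

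**What the plan says.** On when AE collection ends:

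- Protocol 10.1: "All AEs will be recorded by the Investigator from the time the subject signs informed consent until 28 days after hospital discharge".
- Protocol 8.1.11: "Adverse events will be collected from the time of signing the ICF through Day 60". Footnote 13 of Table 1 says the same, and the SAP's copy of the schedule repeats it: "AEs will be collected from the time of informed consent to Day 60".
- Protocol 4.1 names only the Day 28 contact: "Subjects will be contacted on Day 28 to collect any additional AEs and follow-up for unresolved AEs".

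On the Day 60 call:

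- The synopsis describes "a telephonic contact on Day 60 to collect any additional AEs and follow-up for unresolved AEs to resolution".
- Section 8.2.6 lists, for AEs, only "Update status on previously unresolved AEs". Section 8.2.5, for the Day 28 visit, does list collection of AEs.
- In Table 1 the AE row is marked from screening to Day 28 and is empty in the column headed "Telephone Follow-up at Day 60 and 90". SAP Appendix 1 shows the same empty cell.

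On which AEs are counted, protocol 9.4.4 defines TEAEs twice: once with no end, and once ending 28 days after the investigational product. SAP 10.1 has only the open-ended version: "Treatment-emergent adverse events (TEAE) will be defined as any AE occurring post first administration of study drug". It summarises TEAEs as counts and percentages of subjects, with no allowance for time at risk. SAP 1.0 says the SAP's analyses take precedence over those in the protocol.

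**The concern.** Sites cannot follow 10.1 and 8.1.11 together. Under 8.1.11 every subject has the same nominal window. Under 10.1 the window closes at a time set by discharge, and days in hospital up to Day 28 is a secondary endpoint (protocol 3.2.2) that treatment may change. An arm with shorter stays would be observed for AEs for less time, and a crude percentage would make it look safer with no true difference. If sites choose different rules, the variation between sites adds noise.

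The SAP does not settle the matter. With no TEAE end date, its tables contain whatever each site recorded. Safety and tolerability is a secondary objective, so these tables are a main output of the trial.

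**Working it through.** The plan states no figure to reproduce here. The check is date arithmetic followed by an illustration on assumed inputs.

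**Step 1. Window under each rule.** Rule A (10.1): end day = discharge day + 28. Rule B (8.1.11, footnote 13): end day = 60. The third row uses the second TEAE definition in 9.4.4. It reads the 28 days as running from the last dose, with dosing stopping at Day 14 or at discharge if sooner (6.2): min(14, discharge day) + 28.

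| Discharge day | 5 | 7 | 14 | 20 | 28 | 32 | 40 |
|---|---|---|---|---|---|---|---|
| Rule A end day | 33 | 35 | 42 | 48 | 56 | 60 | 68 |
| Rule A minus Day 60 | -27 | -25 | -18 | -12 | -4 | 0 | +8 |
| 9.4.4 TEAE end day | 33 | 35 | 42 | 42 | 42 | 42 | 42 |

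The two rules agree only for discharge on Day 32. Earlier discharge shortens the window and later discharge lengthens it. On this reading the 9.4.4 definition also varies with stay, for discharge before Day 14.

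**Step 2. Effect on a crude percentage.** Assumptions, none from the documents: the same constant AE hazard h in both arms, every subject in an arm discharged on the same day, no death or dropout, and a 60-day AE risk R of 20%, 40% or 60%. Then h = -ln(1 - R)/60, and the share with at least one recorded AE in a window of w days is P = 1 - exp(-h × w).

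Worked case: R = 40% gives h = 0.5108/60 = 0.00851 per day. Discharge on Day 7 gives w = 35 and P = 25.8%. Discharge on Day 14 gives w = 42 and P = 30.1%. The ratio is 0.857.

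| Discharge day, arm X vs arm Y | Windows (ratio) | R = 20% | R = 40% | R = 60% |
|---|---|---|---|---|
| 7 vs 14 | 35 vs 42 (0.833) | 12.2% vs 14.5%, 0.844 | 25.8% vs 30.1%, 0.857 | 41.4% vs 47.3%, 0.875 |
| 10 vs 14 | 38 vs 42 (0.905) | 13.2% vs 14.5%, 0.911 | 27.6% vs 30.1%, 0.919 | 44.0% vs 47.3%, 0.930 |
| 7 vs 21 | 35 vs 49 (0.714) | 12.2% vs 16.7%, 0.733 | 25.8% vs 34.1%, 0.755 | 41.4% vs 52.7%, 0.786 |

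With 40 subjects per arm, the Day 7 vs Day 14 gap at R = 40% is 0.258 × 40 = 10.3 against 0.301 × 40 = 12.0 subjects, or about 1.7 subjects.

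**Step 3. One fixed window.** With w = 60 for everyone, the windows and the recorded risks are equal, and the ratio is 1.00.

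**The case against.** The strongest reply is that most of the protocol points to a fixed Day 60: 8.1.11, footnote 13 and the synopsis agree, and 10.1 stands alone. This is right as far as it goes. A reader might infer that AE follow-up depends on length of stay however the protocol is applied. The documents do not support that, because the dependence on recording time follows mainly from 10.1. The missing Day 60 item does not create it: if the Day 28 visit were the last collection of new AEs, the end would be fixed for everyone discharged by then. Only subjects still in hospital after Day 28, who are assessed daily, would have longer capture.

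A reader of 8.2.6 and Table 1 might also infer that the Day 60 call collects no new AEs. The synopsis says that it does. The accurate finding is a contradiction about the call.

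Nor do the documents support a conclusion that late serious harms are lost. Under 10.1 and 10.5, SAEs are reported from consent to the last study visit regardless of discharge, and survival and new hospital or ICU stays are asked about at Days 28, 60 and 90. The problem concerns non-serious AEs.

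Three further points stand in part:

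- Because dosing ends by discharge, 10.1 still covers at least 28 days after the last dose. That is reasonable coverage of exposure, but it does not equalise the arms.
- No visit is scheduled at discharge + 28, so the Step 1 cut-offs are nominal, and what is captured depends on what sites ask and when.
- A constant hazard is doubtful in patients who are most ill early. If AEs cluster early, the bias is smaller than shown.

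Finally, the SAP cites protocol V5.0 and the protocol supplied is V4.0, so 10.1 may have been corrected. The SAP's own schedule still has Day 60 in the footnote and no mark in the column.

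**Conclusion.** The point holds as an internal contradiction with a conditional bias. The protocol gives two incompatible ends to AE collection and two accounts of the Day 60 call, and the SAP neither chooses between them nor sets a TEAE end date.

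If 10.1 is followed, discharge on Day 5 or Day 20 closes the non-serious AE window 27 or 12 days before Day 60, and window length is tied to a secondary endpoint. For an assumed discharge on Day 7 vs Day 14, the artefact is a risk ratio of 0.844 to 0.875. Across the other discharge pairs tried, it runs from 0.733 to 0.930. It favours the arm with shorter stays, and its size rests wholly on the assumed discharge days, constant equal hazards and 60-day risks. If Day 60 is applied and the call asks about new AEs, this difference in window disappears. Confidence is moderate because of the version mismatch.

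**What to change.** 1. Change protocol 10.1 to end AE recording at Day 60, as 8.1.11, footnote 13 and the synopsis already state.
2. Add collection of new AEs to 8.2.6, and mark the AE row of Table 1 for the Day 60 call. The column is shared with Day 90, so the mark should be limited to Day 60. Make the same change in SAP Appendix 1, and align the Day 28 wording in 4.1.
3. State in SAP 10.1 one fixed AE and TEAE end day common to both arms, and remove the double TEAE definition from protocol 9.4.4.
4. First check whether protocol V5.0 already makes any of these changes.

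The cost is amendment wording and one question on a call that is already made. The downside is slightly more AE data entry.
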